6.5.7 Carboplatin Administration and Dose Adjustments

Carboplatin may be substituted for cisplatin if a patient develops 1) grade 3 or higher ototoxicity, 2) grade 2 or higher peripheral neuropathy, or 3) an unacceptable cisplatin-associated nausea and vomiting after receiving 1 or 2 doses of cisplatin. In the event of carboplatin-induced ≥ 3 neurotoxicity, carboplatin is discontinued.

Carboplatin is available commercially. It should be stored and reconstituted according to standard pharmacy operating procedures.

Carboplatin will be infused over 1 to 2 hours. Carboplatin dosage (mg) will be calculated for a target AUC 6 using the Calvert formula (table 9). Creatinine clearance (CrCl) will be calculated using the Cockcroft-Gault equation (table 10).

For females, use 85% of the calculated CrCl value. The actual body weight in kilograms will be utilized in the Cockcroft-Gault formula (table 10). However, if the calculated creatinine clearance exceeds an upper limit for creatinine clearance, as specified below, then this ceiling value for creatinine clearance, rather than the calculated creatinine clearance, will be used in the Calvert formula to calculate the dose of carboplatin. The maximum creatinine for both male and female patients is 125ml/min. Alternatively, at the treating physician's discretion, a measured 24-hour creatinine clearance can be obtained. In this case, the measured creatinine clearance can be used to calculate the carboplatin dose in the Calvert formula (table 9).

Table 9. Calvert formula for calculation of carboplatin dosage

$\text{Dose of carboplatin (mg)} = \text{AUC} \times [\text{CrCl (ml/min)} + 25]$

Table 10. Cockcroft-Gault equation for calculation of creatinine clearance (CrCl)

$$\text{CrCl (ml/min)} = \frac{(140 - \text{age}) (\text{wt kg})^*}{72 \times \text{serum creatinine (mg/dl)}}$$

* For female, the equation needs to be multiplied by 0.85.

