6.5.6.2 Thrombocytopenia

Chemotherapy must not be administered until platelets are $\geq 100,000$. If chemotherapy must be withheld due to thrombocytopenia, platelet counts should be obtained weekly until the counts reach the lower limits for treatment as outlined. Treatment is based upon the nadir count of the last cycle of chemotherapy as follows:

Table 7. Cisplatin dose modifications in thrombocytopenia

Nadir of last cycle		% Dose of cisplatin from starting dose
	Platelets on day 1 of each cycle < 100,000	Platelets on day 1 of each cycle ≥ 100,000
$\geq 50,000$	Hold	100%
< 50,000 (1 st occurrence)	Hold	80%
< 50,000 (2 nd occurrence)	Hold	60%

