6.5.6.3 Peripheral neuropathy

-

A neurological examination must be performed at least before entry into the study and then once every cycle and when the patient goes off chemotherapy. In case of symptoms or signs experienced by the patient, more frequent examinations should be performed and dose modification will be as follows:

Grade 0 - 1: no change

Grade ≥ 2 : Decrease cisplatin dose by 50%. Carboplatin at an AUC of 6 may be substituted for cisplatin

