6.5.6.4 Otoxicity

Cisplatin is known to cause high frequency hearing loss. If grade 1 or 2 hearing loss occurs, the risk of additional hearing loss versus the potential benefit of continuing cisplatin chemotherapy should be made. If cisplatin is to be continued in the presence of grade 1 or 2 hearing loss, the dose of cisplatin should be decreased by 50%. Grade 3 and 4 hearing loss is an indication to discontinue the drug. In case of grade 3 or 4 toxicity, carboplatin (at dosage of AUC 6) may be used to replace cisplatin in the remaining chemotherapy cycles. The dose of carboplatin AUC 6 will be calculated based on the Calvert formula (table 9).

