6.5.6.5 Nephrotoxicity

If, despite adequate rehydration, serum creatinine increases to \geq grade 1 ($> 1.5 \times$ ULN), creatinine clearance should be recalculated before the next cycle and subsequent dose reductions will be considered as follows:

Table 8. Cisplatin dose modifications in kidney impairment

Calculated creatinine clearance (ml/min)		% Dose of cisplatin from starting dose
≥ 60		100%
< 60	0% (withhold treatment for a maximum of 2 weeks and repeat serum creatinine weekly after additional hydration), then	
	If *CCl was < 60 mL/min and is now:	The percent dose to give is:
	> 50 but < 60	80%

-	≥ 40 and ≤ 50	50%
	< 40	0%

* CCl = creatinine clearance

If creatinine clearance recovers, the dose of cisplatin for the following cycle should be re-escalated to the previous dose level.

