6.5.7.1 Thrombocytopenia

Carboplatin must not be administered until platelets are $\geq 100,000/\text{mm}^3$. Treatment is based upon the nadir count of the last cycle of chemotherapy as follows:

Table 11. Carboplatin dose modifications in thrombocytopenia

Nadir of last cycle	Dose of carboplatin	
	Platelets on day 1 of each cycle < 100,000	Platelets on day 1 of each cycle $\geq 100,000$
$\geq 50,000$	Hold	AUC 5
< 50,000	Hold	AUC 4

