6.5.7.2 Neutropenia

Carboplatin must not be administered until ANC $\geq 1500/\text{mm}^3$.

Table 12. Carboplatin dose modifications in neutropenia

Nadir of last cycle	Dose of carboplatin	
	ANC on day 1 of each cycle < 1500	ANC on day 1 of each cycle ≥ 1500
Febrile neutropenia	Hold	AUC 6
< 500 for < 5 days	Hold	AUC 6
< 500 for ≥ 5 days	Hold	AUC 4

6.5.8 5-Fluorouracil Dose Adjustments

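### Table 11's two platelet-nadir rows cover every nadir and neither gives AUC 6, so read literally the stated carboplatin target can never be given

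*Combined protocol and SAP*

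**What the plan says.** Carboplatin is an optional substitute for cisplatin after certain toxicities, and the text gives its dose three times as AUC 6:

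- Section 6.5.6.3, for neuropathy: "Carboplatin at an AUC of 6 may be substituted for cisplatin".
- Section 6.5.6.4, for hearing loss: "carboplatin (at dosage of AUC 6) may be used to replace cisplatin in the remaining chemotherapy cycles".
- Section 6.5.7, for carboplatin in general: "Carboplatin dosage (mg) will be calculated for a target AUC 6 using the Calvert formula".

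Section 6.5.7.1 then ties the dose to platelets: "Treatment is based upon the nadir count of the last cycle of chemotherapy as follows". The table that follows, "Table 11. Carboplatin dose modifications in thrombocytopenia", holds treatment if day-1 platelets are below 100,000. Otherwise it gives AUC 5 after a nadir of 50,000 or more and AUC 4 after a nadir below 50,000.

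Section 6.5.7.2 has a separate table, "Table 12. Carboplatin dose modifications in neutropenia". Once the neutrophil count has recovered, it gives AUC 6 after febrile neutropenia or after a count below 500 for less than 5 days. After a count below 500 for 5 days or more it gives AUC 4.

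**The concern.** A modification table should leave the full dose in place for a patient who did not have the toxicity. Table 11 does not, because its upper row starts at 50,000 and has no upper limit. The text points to AUC 6 and the table to AUC 5 for the same patient.

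Under section 6.0, chemotherapy may be given at any participating institution, so more than one team has to interpret this. Two teams could give doses one-sixth apart to identical patients, each following the protocol. One would be under the stated target. The other would be over the table, possibly in a patient whose platelets had fallen.

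**Working it through.** The plan gives no figure of its own to reproduce here. The check compares the dosing rules and then sizes the gap with the protocol's formula.

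**Inputs**
- Target: AUC 6 (sections 6.5.6.3, 6.5.6.4, 6.5.7).
- Dose in mg = AUC × (creatinine clearance + 25) (Table 9).
- Clearance values: 60 ml/min is the entry minimum (section 3.1.7), and 125 ml/min is the ceiling for calculated clearance (section 6.5.7). The value of 90 is only an illustration between them.

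**1. Does Table 11 leave any nadir uncovered?** No. A nadir is either 50,000 or more, or below 50,000. The only possible results are hold, AUC 5 and AUC 4.

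**2. Is the first carboplatin dose exempt?** Not as written. The rule refers to the last cycle of chemotherapy, not of carboplatin. Section 6.5.7 allows the switch only once a toxicity has developed, so an earlier chemotherapy nadir will normally exist.

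**3. Size of the gap**

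| Clearance (ml/min) | AUC 6 | AUC 5 | Gap |
|---|---|---|---|
| 60 | 6 × 85 = 510 mg | 5 × 85 = 425 mg | 85 mg |
| 90 | 6 × 115 = 690 mg | 5 × 115 = 575 mg | 115 mg |
| 125 | 6 × 150 = 900 mg | 5 × 150 = 750 mg | 150 mg |

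The ratio is 5/6 = 0.833 at every clearance, a shortfall of 16.7%.

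**4. Comparison with Table 12.** Its rows begin at febrile neutropenia or a neutrophil count below 500. A patient with neither falls outside the table and keeps the AUC 6 of the text. Table 11 has no such outside. Every patient to whom Table 12 gives AUC 6 also falls in a Table 11 row giving AUC 5 or AUC 4, and nothing says which table governs.

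**5. Comparison with the cisplatin tables**

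| Situation, day-1 counts recovered | Cisplatin, % of starting dose | Carboplatin, % of AUC 6 |
|---|---|---|
| Platelet nadir 50,000 or more | 100% (Table 7) | 5/6 = 83.3% (Table 11) |
| First platelet nadir below 50,000 | 80% (Table 7) | 4/6 = 66.7% (Table 11) |
| Neutrophils below 500 for 5 days or more | 80% (Table 6) | 4/6 = 66.7% (Table 12) |

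Carboplatin is cut harder in both of the lower rows, where both drugs are reduced.

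**6. Effect on the statistics.** Section 11.0 measures chemotherapy compliance by the number of courses received. The completion test in section 12.0 uses 25 patients, a minimum of 18 completers, and rates of 55% and 77%. None of these depends on the carboplatin dose.

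**The case against.** The strongest reply is that Table 11 is a modification table, headed and titled for thrombocytopenia, so it comes into play only after a platelet fall. The sequence is then orderly: AUC 6 to start, AUC 5 after a lesser fall, AUC 4 after a nadir below 50,000. The literal reading would also cancel the AUC 6 in three sections and in Table 12, which makes it the less natural one.

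This stands as a plausible account of the intent. It does not supply the missing rule, because no platelet level says when a patient enters the table or when AUC 6 continues. The title does not settle it either. The cisplatin table has the same wording, "Table 7. Cisplatin dose modifications in thrombocytopenia", and its row for 50,000 or more is plainly a catch-all that means no reduction.

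A reader might infer from Table 7 that AUC 5 is a misprint for AUC 6. The documents do not support that. Table 7 doses another drug, and carboplatin is cut harder than cisplatin in both comparable reduction rows, which fits an intended AUC 5 at least as well. Raising the cell to AUC 6 for every nadir down to 50,000, on that parallel alone, would also be less cautious than bounding the row.

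It can also be said that each table deals with one toxicity, so that AUC 6 in Table 12 means only no cut for neutropenia. The cisplatin rules overlap in the same way without a stated order. That is fair, and it makes the precedence rule a secondary clarification. It is still needed: even on the step-down reading, a moderate platelet nadir with brief neutropenia gives AUC 5 from one table and AUC 6 from the other.

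**Conclusion.** The point holds as an internal contradiction in the dosing rules. Followed as written, Table 11 never lets a patient reach the AUC 6 target, and a patient with no thrombocytopenia gets 16.7% less than that target at any clearance. This rests on reading the upper row without a limit, which is how it is printed; the table appears complete.

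Which dose was meant cannot be decided from the documents.

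A reader might also infer that the primary compliance result is at risk. It is not: a course counts as a course at either dose, so sample size, error rates and the completion count are unaffected. The effect is confined to patients switched to carboplatin. The documents do not say how many that will be; in a trial of 25 patients, with carboplatin only an optional substitute, I assume few. It should be corrected because the dosing instruction is ambiguous and the correction is cheap.

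**What to change.** Amend section 6.5.7.1 as follows:

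- Add a row to Table 11 giving AUC 6 when the last-cycle platelet nadir is above a stated level, and limit the AUC 5 row to nadirs from 50,000 up to that level. The clinical team sets the level.
- Alternatively, if the clinical team confirms that AUC 5 is a misprint, change that cell to AUC 6.
- In either case, state that the lower dose applies when Tables 11 and 12 give different doses.

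The cost is amendment wording only, with no change to sample size, visits or data collected.

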6.5.7.1 Thrombocytopenia

Carboplatin must not be administered until platelets are $\geq 100,000/\text{mm}^3$. Treatment is based upon the nadir count of the last cycle of chemotherapy as follows:

Table 11. Carboplatin dose modifications in thrombocytopenia

Nadir of last cycle	Dose of carboplatin	
	Platelets on day 1 of each cycle < 100,000	Platelets on day 1 of each cycle $\geq 100,000$
$\geq 50,000$	Hold	AUC 5
< 50,000	Hold	AUC 4

6.5.7.2 Neutropenia

Carboplatin must not be administered until ANC $\geq 1500/\text{mm}^3$.

Table 12. Carboplatin dose modifications in neutropenia

Nadir of last cycle	Dose of carboplatin	
	ANC on day 1 of each cycle < 1500	ANC on day 1 of each cycle ≥ 1500
Febrile neutropenia	Hold	AUC 6
< 500 for < 5 days	Hold	AUC 6
< 500 for ≥ 5 days	Hold	AUC 4

6.5.8 5-Fluorouracil Dose Adjustments

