6.5.6 Cisplatin Dose Adjustments

6.5.6.1 Neutropenia

Treatment can be delayed for up to 2 weeks until ANC is $\geq 1500/\text{mm}^3$. However, if the counts have not recovered in 2 weeks, the patient should go off chemotherapy. Dose reductions for reduced ANC are not based on a single nadir count. The ANC must remain $< 500/\text{mm}^3$ for > 5 days before a dose reduction is made. If the results of the scheduled weekly complete blood count documents an ANC of $< 500/\text{mm}^3$, repeat counts are to be obtained every other day until the ANC recovers to a level of $> 500/\text{mm}^3$. If chemotherapy must be withheld due to neutropenia, complete blood count should be obtained weekly until the counts reach the lower limits for treatment as outlined.

Table 6. Cisplatin dose modifications in neutopenia

Nadir of last cycle		% Dose of cisplatin from starting dose
	ANC* on day 1 of each cycle < 1500	ANC* on day 1 of each cycle ≥ 1500
Febrile neutropenia (regardless of duration)	Hold	100%
< 500 for < 5 days	Hold	100%
< 500 for ≥ 5 days	Hold	80%

* ANC = absolute neutrophil count

ANC must be $\geq 1,500/\text{mm}^3$ on day 1 of each cycle. Reduce doses only for ANC is $< 500/\text{mm}^3$ for ≥ 5 days.

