6.5.8.3 Hematologic

For grade 2 or higher hematologic toxicities, 5-fluorouracil dose will be reduced by 20% from 1000 to 800 mg/m²/day. For grade 2 or higher hematologic toxicities as a second occurrence, 5-fluorouracil dose will be reduced from 800 to 640 mg/m²/day.

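### Table 12 gives two carboplatin doses after febrile neutropenia lasting 5 days or more, and section 6.5.6.1 states two duration cut-offs for reducing cisplatin

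*Combined protocol and SAP*

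**What the plan says.** Carboplatin after a low neutrophil count is governed by section 6.5.7.2 and its "Table 12. Carboplatin dose modifications in neutropenia". The dose waits until the ANC reaches 1500. After recovery, febrile neutropenia leads to AUC 6, an ANC below 500 for under 5 days also leads to AUC 6, and "< 500 for ≥ 5 days" leads to AUC 4. The section contains no other rule.

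Table 6 in section 6.5.6.1 has the same three rows for cisplatin, giving 100%, 100% and 80% of the starting dose. Its first row is labelled "Febrile neutropenia (regardless of duration", followed by a closing bracket. Table 12 has no counterpart to the words in that bracket.

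The text above Table 6 says that the ANC must stay below 500 "for > 5 days before a dose reduction is made". The line under the table, which begins "Reduce doses only for ANC is", puts the limit at 5 days or more, as the table does.

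**The concern.** A dose-modification table should return one dose for each clinical picture. Table 12 returns two for a patient who has both fever and prolonged neutropenia. The cisplatin rule returns two for an afebrile patient at the boundary of 5 days.

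Section 6.0 lets patients receive chemotherapy at any participating institution. Two sites could therefore follow the same page correctly and give different platinum doses after the same episode. At stake are dosing safety and consistency between sites. The trial's hypothesis tests are not involved.

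**Working it through.** No sample size or error rate is involved, so the check is whether the rows exclude one another, followed by the dose arithmetic.

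**1. Rows side by side, day-1 ANC at least 1500**

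| Nadir of last cycle | Table 6, cisplatin | Table 12, carboplatin |
|---|---|---|
| Febrile neutropenia | 100%, stated for any duration | AUC 6, duration not mentioned |
| ANC below 500, under 5 days | 100% | AUC 6 |
| ANC below 500, 5 days or more | 80%, fever not mentioned | AUC 4, fever not mentioned |

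Rows 1 and 2 overlap harmlessly, because the dose is the same. Rows 1 and 3 overlap with different doses. In Table 6 the qualifier in row 1 tells the reader to set duration aside once there is fever, which gives 100%. In Table 12 nothing decides.

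**2. Size in Table 12 read alone**

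The Calvert formula (Table 9) is dose = AUC × (clearance + 25). The gap between AUC 6 and AUC 4 is 2 × (clearance + 25) mg, one third of the AUC 6 dose.

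- Clearance 60 ml/min: 6 × 85 = 510 mg against 4 × 85 = 340 mg.
- Clearance 100 ml/min: 6 × 125 = 750 mg against 4 × 125 = 500 mg.
- Clearance 125 ml/min: 6 × 150 = 900 mg against 4 × 150 = 600 mg.

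These clearances are illustrative. The value 60 is the entry criterion in section 3.1.7, and Table 8 expects lower values on treatment. The value 125 is the ceiling that section 6.5.7 sets for calculated clearance; a measured 24-hour value may be used instead.

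**3. Size if the platelet table is applied as well**

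"Table 11. Carboplatin dose modifications in thrombocytopenia" gives AUC 5 for a nadir of 50,000 or more and AUC 4 below that. The protocol does not say how it combines with Table 12. Assume that the lower dose governs:

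- Nadir 50,000 or more: min(6, 5) = 5 against min(4, 5) = 4. That is 425 against 340 mg at clearance 60, 625 against 500 mg at 100, and 750 against 600 mg at 125, a 20% difference.
- Nadir below 50,000: min(6, 4) = 4 against min(4, 4) = 4, no difference.

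**4. The cisplatin cut-off**

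Take an afebrile patient with an ANC below 500 for exactly 5 days, recovered on day 1. By the text, 5 is not more than 5, so there is no reduction and the dose is 100%. By Table 6, 5 is at least 5, so the dose is 80%.

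- Concurrent phase: 100 against 0.8 × 100 = 80 mg/m².
- Adjuvant phase: 80 against 0.8 × 80 = 64 mg/m².

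Both rules depend on the previous cycle's nadir, so only cycles 2 to 6 can be affected.

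**The case against.** The strongest reply concerns Table 6. A reader might infer that it contradicts itself in the same way as Table 12, or that the line under it requires a reduction in every prolonged case. The documents do not support either reading. The qualifier on the febrile row addresses the overlap directly. The line under the table limits when a reduction may be made; it does not order one. That fever plus prolonged neutropenia then earns a larger next dose than the same neutropenia without fever is a clinical objection, not a contradiction.

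It can also be said that Table 12 copies the row order and the full/full/reduced pattern of Table 6, so the intent carries over. That is a fair indication. But there is no cross-reference, the qualifier is absent, and a site cannot tell whether it was dropped on purpose.

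On the cut-off, section 6.5.6.1 asks for counts weekly and then every other day once the ANC is below 500. With the first low count on day 0, repeats fall on days 2, 4 and 6, so an elapsed time of exactly 5 days will seldom be seen. Counting the first low day as day 1 puts repeats on days 3, 5 and 7, and a fifth low day can then be recorded. The case is uncommon, but the two rules still differ.

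The practical limits stand:

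- Treatment is held until the ANC recovers.
- Carboplatin is reached only by substitution under section 6.5.7.
- In adjuvant cycles section 6.5.8.3 separately lowers the other drug: "For grade 2 or higher hematologic toxicities, 5-fluorouracil dose will be reduced by 20% from 1000 to 800" mg/m²/day. If an ANC below 500 counts as grade 2 or higher, the adjuvant regimen would not be given wholly unreduced.

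**Conclusion.** Two conflicts in operative dosing rules are confirmed: the overlap of the febrile and prolonged rows in Table 12, and the differing 5-day cut-offs within section 6.5.6.1. The cisplatin overlap in Table 6 is not a third conflict, because its own wording points to full dose.

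The carboplatin gap is one third if Table 12 is read alone. It is one fifth or nil if Table 11 also applies and the lower dose governs, which is an assumption. The cisplatin gap is 20 percentage points of the starting dose at exactly 5 days. The documents give no rate for such episodes; few patients are likely to be affected.

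A reader might infer an overdose risk or an effect on the primary comparison. Neither follows. No reading exceeds the full protocol dose. Section 11.0 measures chemotherapy compliance by courses received, so a reduced-dose course still counts, and the decision rules in section 12.0 are unchanged. Severity is minor.

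**What to change.** In the section 6.5.6.1 text, change > 5 days to ≥ 5 days, to match Table 6 and the line under it.

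In Table 12, separate the febrile and prolonged rows by one of two explicit edits:

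- **Carry over Table 6's rule.** Mark the febrile row as applying whatever the duration, and the prolonged row as applying without fever.
- **Take the more cautious dose.** Add *with or without fever* to the prolonged row and *unless < 500 for ≥ 5 days* to the febrile row, and use the same wording in Table 6. Febrile cases with a nadir of 500 or more keep a row.

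The choice is clinical and belongs to the sponsor. The cautious option costs a lower platinum dose for a few patients.

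Do not add a general rule that the lower of two table doses governs. Table 11 gives AUC 5 or AUC 4 at every platelet nadir, so such a rule would remove AUC 6 after any recorded nadir, against the AUC 6 target in section 6.5.7. That conflict needs its own resolution.

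The cost is one amendment with a few words and one symbol. No procedure is added and no statistical figure changes.

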6.5.8.1 Mucositis

In case of grade 3 mucositis lasting more than 96 hours or grade 4 mucositis, 5-fluorouracil dose will be reduced by 20% from 1000 to 800 mg/m²/day. A mouth rinse should always be allowed.

In case of grade 3 mucositis lasting more than 120 hours as a second occurrence or grade 4 mucositis as a second occurrence, the dose of 5-fluorouracil will be reduced to 800 mg/m²/day for 3 days.

6.5.8.2 Diarrhea

In the case of severe diarrhea, octreotide is recommended. If the patient has a significant diarrhea occurrence again (> 3 loose stools/24 hr), the patient should be treated prophylactically in the subsequent cycles with 2 tablets of loperamide or diphenoxylate in addition to 1 or 2 tablets after each loose stool. The maximum daily dose of loperamide is 16mg and diphenoxylate is 20mg/day.

For grade 4 diarrhea, or grade 3 diarrhea lasting > 7 days despite the prophylactic treatment, 5-fluorouracil will be reduced by 10% per day from 1000 mg/m²/day to 900 mg/m²/day for subsequent cycles. Appropriate symptomatic treatment with loperamide or diphenoxylate hydrochloride with atropine sulfate should be given.

If despite these measures, grade 4 diarrhea or grade 3 diarrhea lasting > 7 days occurs again, the dose of 5-fluorouracil will be reduced 20% from 1000 mg/m²/day to 800 mg/m²/day in the subsequent cycle.

